UT-S/PMH and OHSU research team members will survey family members of trauma patients to compare the quality of communication for severely injured geriatric trauma patients cared for by trauma teams. When possible, UT-S/PMH and OHSU will survey patients on their quality of life. UT-S/PMH and OHSU will survey the patient’s primary nurse on the quality of communication patients and will survey patient’s families about their thoughts on the quality of communication as well. UT-S/PMH and OHSU will survey trauma unit staff before and after clinicians learn to use the best case/worst case tool, to assess whether the communication intervention improves feelings of moral distress. UT-S/PMH and OHSU will use chart review to collect downstream clinical outcomes including intensity of treatment and receipt of palliative care. UT-S/PMH and OHSU will archive de-identified graphic aids used by trauma surgeons with intervention patients to explore how the intervention was enacted.

Background and Significance

Improvements in medical care that have increased life expectancy have shifted the end-of-life trajectory for older adults who are now increasingly vulnerable to traumatic injury.¹ Each year, half a million older adults will suffer injury from a fall or car crash, making it the fifth leading cause of death. Older adults fare far worse than younger patients with similar injuries due to presence of chronic comorbid conditions and reduced physiologic reserve.²⁻⁴ Traumatic injury is often a terminal event that leads to a 20% in-hospital and 40% one-year mortality.⁵ Severely injured older adults undergo a series of invasive surgical interventions furthering a course of care—including prolonged life support³ or confinement in a nursing home—that is often inconsistent with patients’ preferences and goals. Given the burdens of treatment and poor prognosis, severely injured older adults would benefit from decision support interventions to facilitate early access to palliative care which can reduce unwanted invasive procedures, address symptoms and clarify long-term goals.^{6,7}

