We will conduct a pre/post interventional study at the trauma centers within OHSU and UT-S/PMH. Research team members at UT-S/PMH and OHSU will recruit 50 patients in the control arm and 50 patients in the intervention arm, aiming to balance patients who receive usual care with those who receive intervention from each participating surgeon. As close as possible to 72 hours of injury, study staff at UT-S/PMH and OHSU will administer the Quality of Communication (QOC) questionnaire family version⁴⁰ to the patient's family member present (study partner) for care discussions. At 10 days post-admission, study staff will administer The Family Inpatient Communication Survey (FICS)⁴¹ and the Goal Concordant Care survey⁴². At thirty days after admission, if the patient is still living and has DMC, they will be given The Trauma Quality of Life (T-QoL)⁴³ survey and their enrolled family member will complete an adapted T-QoL. If the patient is alive but lacks DMC at 30 days after admission, their family member will complete an adapted T-QoL. If the patient has died by 30 days after admission, the Family Member will only complete the first two family member surveys. Study staff at UT-

S/PMH and OHSU will conduct chart reviews 30 days after admission to record treatments received including surgery, intensive care unit days and palliative care.

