Chart reviews will be conducted at 10 and 30 days after admission by research team members at UT-S/PMH and OHSU. Team members will use the Therapeutic Intervention Scoring System to guide chart data abstraction in order to measure treatment intensity for the first 10 days after injury.⁵¹⁻⁵⁵ We will record the number and duration of life supporting treatments received⁵⁶ within 30 days of admission using six well described data fields: intubation and mechanical ventilation, tracheostomy, feeding tube insertion, hemodialysis, enteral or parenteral nutrition, and cardiopulmonary resuscitation. We will also record measures of high quality palliative care including initiation and timing of palliative care consultation, documentation of care preferences within 48 hours of admission, timing of Do Not Resuscitate orders and discharge to Hospice.⁵⁷ We will collect the following patient-level covariates: Injury Severity Score, GTOS, TRISS for patients age 50-64, pre-existing comorbid illnesses, age, race and ethnicity, gender, insurance status, educational attainment.

Best case/worst case graphic aid retention

[figure not shown]
A coded digital image of the graphic aid that accompanies the communication intervention (labeled only with study ID number) will be archived by research team members at UT-S/PMH and OHSU. This graphic aid is created as part of the intervention and before it is given to the patient's family a member of the research or clinical teams will take a picture of it for archival.

Primary outcomes: **Primary outcome:** The QOC questionnaire⁴⁰ is a 19-item scale with two domains: general communication (8 items) and end-of-life communication (11 items). The instrument is available in patient-specific and family member-specific versions and has acceptable internal consistency and construct validity.

Data analysis plan: The intervention effect, QOC, will be tested in the framework of generalized linear mixed effects models^{58,59} comparing the pre-intervention with post-intervention periods with a treatment dummy variable, surgeon random effect, and site dummy variables to control for site-specific effect. UW analysts will adjust for covariates to increase the

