statistical precision of our treatment effect estimation. Our exploratory analyses will examine other patient endpoints such as intensity of treatment and palliative care received. We will use linear mixed effects models for continuous responses, logistic random effects models for binary responses and log-linear random effect models for count-dependent variables.

Schedule of Events

★ Patient/family will be approached as close as possible to 24-48 hours post-admit (up to 7 days post-injury) and F1/N1 surveys will be conducted as close as possible to 72 hours post-admit.

Incentives

Trauma providers

Focus groups: To compensate participants for their time during the focus groups, each participant will receive \$200 at the completion of the focus group.

Best case/worst case tool training: To encourage surgeons to participate as research subjects in the “Best Case/Worst Case” training session, incentives will be required as the training will take 2 hours of their time. Using incentives with physicians as research subjects is well-documented in the survey-research literature. Participation is significantly more likely with increased remuneration.^{60,61} Previously, about \$250 per physician has proven a successful incentive for our research; this is the amount given to participants in our surgeon focus groups. We will be giving surgeons \$245 for their time so we do not have to collect social security numbers from surgeon participants at OHSU (\$250 is a common limit for collecting social security numbers from research participants). In addition, we will provide refreshments for surgeons who participate in the training sessions at UT-S/PMH and OHSU. Surgeons will receive incentives only for participating in the training as the intervention requires modest effort beyond the usual care surgeons provide to patients.

Trauma provider interviews following best case/worst case tool training: No incentive is provided for those participating in the interview. *Nurse survey:* UT-S/PMH and OHSU research team members will give \$5 to nurses upon completion of each QOC survey.

Moral distress survey: No incentive is provided for those participating in the moral distress survey.

Family members and patients

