Family Member Participant Incentives: OHSU research team members will give family member participants \$15 for completing the first survey and \$10 for the second survey. Family members who complete the third survey will receive an additional \$10 for a maximum incentive of \$35.

UT-S/PMH research team members will give family member participants \$24 for completing the first survey. Incentives given to family members at UT-SW are lower than at OHSU because UT-SW requires researchers to collect social security numbers and use ClinCards for incentives of \$25 or more. To avoid burdening family members by asking for social security numbers and by including the off-putting ClinCard language in their consent form, we have reduced their total incentive.

At both sites, patients will not receive any compensation for participating in this study. If the family member providing surrogate consent for a patient who lacks DMC and the study partner are *not* the same person, only the study partner will receive incentives.

Statistical Considerations

Sample Size

UT-S/PMH and OHSU research team members will sequentially recruit 50 patients in the control and 50 patients in the intervention arms. Power calculation: Based on current available publications, the standard deviation for the QOC measurement is estimated to be around 3.5. Assuming the between doctor variance accounts for 10% of the total variance, we computed power of 84% to detect a medium-large effect of 2.00 points on the QOC scale, and 96% power to detect a large effect of 2.50 QOC points. If the between doctor variance accounts for 30% of the total variance, the power to detect these effects are 92% and 99% respectively.

Analysis

Analysts at UW will test the intervention effect, QOC, in the framework of generalized linear mixed effects models^{58, 59} comparing the pre-intervention with post-intervention periods with a treatment dummy variable, surgeon random effect, and site dummy variables to control for site-specific effect. We will adjust for covariates to increase the statistical precision of our treatment effect estimation. Our exploratory analyses will examine other patient endpoints such as intensity of treatment and palliative care received. We will use linear mixed effects models for continuous responses, logistic random effects models for binary responses and log-linear random effect models for count-dependent variables.

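### Do the exploratory timing and life-support duration fields need a named time-to-event model and a rule for death and discharge?

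*Combined protocol and SAP*

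**What the plan says.** In the Combined protocol and SAP, the Chart review section lists the palliative fields to be abstracted, including "initiation and timing of palliative care consultation, documentation of care preferences within 48 hours of admission, timing of Do Not Resuscitate orders" and hospice discharge. On life support it says "We will record the number and duration of life supporting treatments received", over a 30-day window from admission. Research Design adds that the 30-day review is to "record treatments received including surgery, intensive care unit days and palliative care".

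The commitment to analyse is narrower. The Data analysis plan and Statistical Considerations (Analysis) carry the same sentence: "Our exploratory analyses will examine other patient endpoints such as intensity of treatment and palliative care received". Project Summary and Timeline describes these outcomes as "downstream clinical outcomes including intensity of treatment and receipt of palliative care". The models offered are "linear mixed effects models for continuous responses, logistic random effects models for binary responses and log-linear random effect models for count-dependent variables", and no field is assigned to any of them. Death is addressed only for the survey schedule. No section says how a patient who dies, leaves hospital, or never has a consultation or DNR order enters a timing or duration variable.

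**The concern.** A time to consultation exists only for patients who have one. If timing were treated as a continuous response, everyone else would drop out, and the comparison would be conditioned on something that happens after the intervention. The arms are enrolled in successive years, so a drift in length of stay or mortality would coincide with the treatment contrast. Death also cuts support days and ICU days short, so fewer days could mean recovery, earlier death, or care limited as the patient wished.

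The trial's own rationale makes this relevant. The conceptual framework expects palliative need to be recognised earlier, and Background and Significance cites 20% in-hospital mortality, which is about 10 of 50 patients per arm. At stake is a missed or spurious secondary statement that palliative care came earlier or that treatment burden fell.

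**Working it through.** The plan gives no figure for these endpoints. Its only calculated figure is QOC power, which does not involve them.

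**1. Match each chart field to the listed models.**

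| Field | Listed model that fits | What is unstated |
|---|---|---|
| Consultation yes/no; hospice discharge | logistic | nothing essential |
| Preferences documented within 48 hours | logistic | nothing essential |
| Treatment intensity score, first 10 days | linear | days after death or discharge |
| Life-support and ICU days | log-linear or linear | death and discharge |
| Time to consultation, time to DNR order | none, unless limited to patients with the event | model, death, discharge, no event |

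The 48-hour measure has a fixed early window, so the plan already holds one usable measure of whether preferences are addressed early.

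**2. What a recipient-only timing comparison would do.** Inputs: 50 per arm (Sample Size). The 30-day horizon is the life-support window, taken here for timing too. The daily hazards are assumptions, because the documents give none. With consultation hazard h, death/discharge hazard c, L = h + c and T = 30:

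- share consulted = (h/L)(1 − e^(−LT))
- mean time among the consulted = 1/L − T·e^(−LT)/(1 − e^(−LT))

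Results:
- h = 0.02, c = 0.08: share 0.2 × 0.950 = 19.0% (9.5 of 50); mean 10 − 1.57 = 8.4 days
- h = 0.04, c = 0.08: share 32.4% (16.2 of 50); mean 7.5 days
- h = 0.02, c = 0.12: share 14.1%; mean 6.7 days

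Doubling the consultation hazard moves the recipient mean by 0.9 days. Faster death or discharge alone moves it by 1.7 days. So the worry about that particular analysis is sound.

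**3. How the candidate tests compare.** These are simulated rejection rates with 4,000 trials per scenario. The two-sided 5% level is assumed, since the plan states none.

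| Scenario (50 per arm) | Recipient-only t-test | Yes/no | Cause-specific log-rank |
|---|---|---|---|
| Consult 0.02 vs 0.04, leaving 0.08 | 7% | 33% | 39% |
| Consult 0.03 vs 0.06, leaving 0.08 | 9% | 38% | 51% |
| Consult 0.03 vs 0.045, leaving 0.08 | 5% | 16% | 20% |
| Null: consult 0.03, leaving 0.06 to 0.12 | 12% | 25% | 5% |
| Null: consult 0.03, leaving 0.08 to 0.10 | 5% | 6% | 4% |
| Null: two severity classes, leaving doubled in the milder class only | 4-5% | 5% | 9-11% |

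In the last row the consultation hazards are 0.005 and 0.06 and do not change by arm. Milder patients leave faster in one arm, so those still at risk there are sicker and the hazard looks higher. Adjusting for site and severity brings rejection to 5% if the true class is known, 7% with a score correlated 0.71 with it, and 9% at 0.45. The plan does collect severity ("Injury Severity Score, GTOS, TRISS for patients age 50-64, pre-existing comorbid illnesses"), but how well those scores would capture it is unknown.

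Enrolment can run to 7 days post-injury. If consultation quadruples the later hazard of leaving and one arm enrols on days 4-7 rather than 1-2, counting from admission rejects 8.6% and entry at enrolment 3.7%. Entry at enrolment cuts power from 50% to 35% when both arms enrol on days 1-7 (0.02 versus 0.04).

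**4. Life-support days.** Assumptions: exponential durations capped at day 30, survivors' mean 8 days, mean time to death 4 days, support until death. The capped means are 8(1 − e^(−3.75)) = 7.81 and 4(1 − e^(−7.5)) = 4.00. Raise mortality from 20% to 30%:

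- All deaths inside a fixed 60% supported: 0.4 × 7.81 + 0.2 × 4.00 = 3.92, then 0.3 × 7.81 + 0.3 × 4.00 = 3.54. Survivors' supported share has also fallen, from 0.4/0.8 = 50% to 0.3/0.7 = 43%.
- Survivors' share held at 50%, all decedents supported: 3.92, then 0.35 × 7.81 + 0.3 × 4.00 = 3.93.
- 60% supported among both survivors and decedents: 4.23, then 4.00.

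The shift therefore runs from a fall of 0.4 days to none, and the largest version rejects 6.5%. With mortality fixed at 20% and all deaths inside the 60% supported, shortening mean time to death from 12 to 9 days lowers recorded days from 5.3 to 4.9 (rejects 5.8%). Halving it to 6 days gives 4.3 (10.5%).

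**The case for a change.** The strongest case for a change is that exploratory results are still read. Leaving the handling of death open until the data are in gives the analyst a free choice, on a theme the rationale itself raises. The team's earlier study, described under Preliminary Studies, found that distress measures depended on highly variable survival. Yes/no is no refuge either: it rejects 25% when death or discharge doubles uniformly. A few added sentences would be cheap.

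Much of this stands. The silence is real, a recipient-only comparison would be a poor choice, and support days should not be interpreted without deaths beside them. What does not stand is the step from there to a prescribed method. The low power belongs to an analysis the plan never adopts. The larger false-positive rates for timing need death or discharge to double between adjacent enrolment years at the same two sites; at 0.08 to 0.10 every test stays between 4% and 6%. A fuller remedy, with severity-adjusted cause-specific hazards, a repeat with late entry, and a surgeon frailty on about 26 events, exchanges one vulnerability for another. Scoring death as zero support-free days could not show shorter support before an expected death, which is one effect the tool might have.

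**Conclusion.** No change to the plan follows. This is unspecified detail on exploratory chart fields that are promised as recorded data, with no between-arm test attached. The named endpoint of palliative care received and the 48-hour preference measure already fit the logistic model. A competent analyst would describe timing as cumulative incidence to day 30 in all patients with chart consent, with death and discharge as competing events, and would show support and ICU days beside deaths by arm. The 30-day chart review already establishes who is alive, and nothing in the plan stands in the way of that description.

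The gain from mandating a time-to-event test is 3 to 13 percentage points of power over yes/no, at absolute power of 20-51%. Against it stands 9-11% rejection under the mixed-severity null, or 7-9% after adjustment for an imperfect score. All of these figures rest on assumed hazards, because the documents give no consultation, DNR or length-of-stay rates. The judgement would change if a between-arm test of timing among recipients, or fewer support days taken alone as a benefit, were put forward as a trial conclusion. The plan proposes neither.
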